#### **4.6 Sensitivity Analyses**

Three sets of sensitivity analyses will be run to help account for the complexities of the COVID-19 pandemic and the CMHC context. In the first set, the analyses for Aims 1-3 will be conducted with (a) treatment completers, (b) patients who completed more than half the number of the suggested sessions (i.e., > 2 sessions for Adapted and > 4 sessions for Standard), and (c) patients who completed half or fewer of suggested sessions. In other words, these analyses will test the effectiveness of TranS-C at varying doses, which may be important considering evidence on “early responders” [104] and “real world” contexts where turnover and dropout can be high [105, 106]. In the second set of sensitivity analyses, we will assess whether any patients who did not complete post-treatment or 6FU had achieved meaningful clinical improvement by mid-treatment, using a reliable change index for the primary

outcome of PROMIS-SD [107]. For the sensitivity analyses, we will define these patients as completers, and we will use their mid-treatment assessment in place of a post-treatment assessment. Then, all pre- to post-treatment analyses for Aims 1-3 will be rerun. In the third set of sensitivity analyses, we will run the analyses for Aims 1-3 but only include post-treatment and 6FU assessments that were collected within 3 months of the target assessment date (e.g., a 6FU assessment that was completed nine months after treatment ended).

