#### 3.4.1 Standard TranS-C

Standard TranS-C is delivered by CMHC providers across eight 50-minute, weekly sessions [40]. It is comprised of 4 cross-cutting modules featured in every session, 4 core modules, and 7 optional modules that are used based on clinical presentation, treatment goals, and provider case conceptualization. The *cross-cutting modules* are case formulation, sleep and circadian education, motivational enhancement, and goal setting. *Core module 1* targets irregular sleep-wake times, difficulty winding-down, and difficulty waking-up. *Core module 2* aims to reduce daytime impairment. *Core module 3* focuses on unhelpful beliefs about sleep. *Core module 4* aims to promote maintenance of changes made during treatment. *Optional module 1* addresses poor sleep efficiency via stimulus control [64] and sleep restriction [65]. *Optional module 2* helps patients reduce time in bed. *Optional module 3* addresses delayed or advanced phase problems (e.g., going to sleep later than desired or waking up earlier than desired). *Optional module 4* helps patients manage worries about sleep. *Optional Module 5* promotes compliance with Continuous Positive Airways Pressure (CPAP) for patients with sleep apnea. *Optional Module 6* helps patients negotiate sleep in complicated environments (e.g., noise from bed/roommates, traffic noise, streetlight entering the bedroom). *Optional Module 7* is for patients who experience nightmares. Training for the Standard TranS-C condition consists of a 1-day workshop (i.e., 6-8 hours) or two, 3-hour training blocks.

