#### 3.4.2 Adapted TranS-C

Adapted TranS-C is delivered by CMHC staff across four, 20-minute, weekly sessions. Treatment consists of the same four *cross-cutting and core modules* as in Standard TranS-C, but the core modules are split up into five, rather than four, modules. *Core module 1* targets irregular sleep-wake times. *Core module 2* targets difficulty winding down. *Core module 3* targets difficulty waking up. *Core module 4* aims to reduce daytime impairment. *Core module 5* promotes maintenance of change. The one *optional module* focuses on reducing sleep-related worry and can be integrated with the core modules, based on clinical presentation, treatment goals, and provider case conceptualization. Training for the Adapted TranS-C condition consists of four, 1-hour workshops or two, 2-hour workshops, based on CMHC preferences.

There have been calls for rigorous approaches to treatment adaptation [66, 67]. In response, we grounded the process for adapting TranS-C in theory, data, and stakeholder input. As the overarching guide for the adaptation process, the Replicating Effective Programs (REP) framework [47] was used. Phase 1 of REP (Pre-Condition) was completed prior to the present protocol. First, as discussed above, we established that

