### 4.2 Dropout

The N by stage of dropout will be reported for the following: dropout after randomization but before the first treatment session, dropout after treatment has begun but attended half or fewer of the intended number of sessions (i.e.,  $\leq 2$  in Adapted,  $\leq 4$  in Standard), dropout after attended more than half the intended number of sessions (i.e.,  $> 2$  in Adapted,  $> 4$  in Standard) but before treatment has been completed, and dropout after treatment has been completed but prior to post-treatment or 6FU assessments. The number of patients who completed a post-treatment assessment but were lost to 6FU will also be reported. When available, the reasons for dropout and improvement among patients who drop out will be reported.

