### 4.3 Aim 1: Effectiveness Outcomes of Standard or Adapted TranS-C versus UC-DT

Multilevel modeling (MLM) [100-102] will be used to account for multiple observations nested within

patient. The level 1 equation will include dummy-coded time indicators as the predictor (0 = pretreatment, 1 = post-treatment). The level 2 equation will include dummy-coded treatment condition (0 = UC-DT, 1 = Adapted or Standard TranS-C), treatment by time interaction terms, and dummy-coded counties (0 = Alameda, 1 = Contra Costa, 2 = Kings, 3 = Monterey, 4 = Placer, 5 = Santa Cruz, 6 = Solano, 7 = Santa Clara, 8 = Santa Barbara, and 9 = Lake) as predictors. The treatment effects of interest will be significant treatment by time interactions at the 5% level on the primary outcome of sleep disturbance and the secondary outcomes of sleep-related impairment, functional impairment, and psychiatric symptoms, all modeled as continuous variables. Significant treatment by time interactions indicate that change in patient outcomes is significantly different comparing Adapted or Standard TranS-C to UC-DT. Significant interactions will be interpreted using planned contrasts (i.e., treatment effects on change from pre-treatment to post-treatment) and graphs. Additionally, the indirect effects of TranS-C relative to UC-DT on functional impairment and psychiatric symptoms through improvements in sleep disturbance and sleep-related impairment will be tested using multilevel structural equation modeling [103].

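### The pooled Aim 1 attendance groups in section 4.6 measure share of the intended course, not dose, and in planned minutes they overlap across the two versions

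*Combined protocol and SAP*

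**What the plan says.** The two versions differ in number and length of sessions. Section 3.4.1: "Standard TranS-C is delivered by CMHC providers across eight 50-minute, weekly sessions". Section 3.4.2: "Adapted TranS-C is delivered by CMHC staff across four, 20-minute, weekly sessions".

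The first set of sensitivity analyses in section 4.6 reruns Aims 1–3 in three attendance groups: (a) treatment completers, (b) patients above half of the suggested sessions, with the cuts given as "i.e., > 2 sessions for Adapted and > 4 sessions for Standard", and (c) "patients who completed half or fewer of suggested sessions". The stated purpose is that "these analyses will test the effectiveness of TranS-C at varying doses". The section does not say whether dose means share of course, number of sessions or minutes. Section 4.2 uses the same version-specific cut for a dropout stage ("attended half or fewer of the intended number of sessions").

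The Aim 1 model in section 4.3 pools the versions: "dummy-coded treatment condition (0 = UC-DT, 1 = Adapted or Standard TranS-C" in brackets. County indicators enter as predictors. The only interaction listed is treatment by time; there is no county-by-time term and no version-by-treatment-by-time term. Section 4.6 does not plan to show the Aim 1 groups by version.

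**The concern.** A cut at half of each version's own course puts patients with very different amounts of planned treatment in the same group, and the plan then describes the comparison in terms of dose. The Background (section 1) uses the word differently. It says that centre staff named dose as a barrier to Standard TranS-C and that Adapted was developed in response. There, dose is the absolute amount of treatment, and the versions differ in it by design.

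In Aims 2 and 3 the versions are the contrast, so they are not mixed. In Aim 1 they are. A difference between the Aim 1 results in two attendance groups can then reflect a different Adapted/Standard mix as well as different attendance. The county indicators do not remove this: as listed, they adjust the level of the outcome, not the treatment-by-time effect that is reported.

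The stake is interpretation. Section 4.6 motivates these reruns by early responders and by settings with high turnover. A pooled result in the lowest group that resembles the result in completers could be read as showing that a brief exposure suffices, when many of the patients in that group had more planned contact than a full Adapted course.

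**Working it through.** **Inputs.** Standard: 8 sessions × 50 min (section 3.4.1). Adapted: 4 sessions × 20 min (section 3.4.2). Cuts: more than 2 (Adapted) and more than 4 (Standard) (section 4.6).

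**The plan's own cuts.** Intended sessions ÷ 2: Adapted 4/2 = 2; Standard 8/2 = 4. Both match section 4.6.

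**Planned minutes = sessions × planned session length.** Full course: Adapted 4 × 20 = 80; Standard 8 × 50 = 400, which is 400/80 = 5 times as long.

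| Group | Adapted | Standard |
|---|---|---|
| (c) half or fewer, at least 1 session | 20, 40 | 50, 100, 150, 200 |
| (b) more than half | 60, 80 | 250, 300, 350, 400 |
| (a) full course | 80 | 400 |

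Section 4.6 does not define completers by a session number; a full course is assumed here, so (a) lies within (b). If patients with no session are counted in (c), its lower end is 0 in both versions and the overlap is unchanged.

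**Order within a version.** Adapted 20–40 is below 60–80; Standard 50–200 is below 250–400. The order is sound.

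**Order across versions.** Standard patients with 2, 3 or 4 sessions (100, 150, 200 min) are in (c) and exceed the full Adapted course of 80. The top of (c) for Standard is 200/80 = 2.5 times a full Adapted course. Standard patients with one session (50 min) do not exceed it.

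**Dependence on version mix.** The documents give no attendance data by version, so the following is illustrative. Assume that sessions are spread evenly within each group.

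- Means in (c): Adapted (20 + 40)/2 = 30; Standard (50 + 100 + 150 + 200)/4 = 125.
- Means in (b), completers included: Adapted (60 + 80)/2 = 70; Standard (250 + 300 + 350 + 400)/4 = 325.
- Ratio (b)/(c) within version: Adapted 70/30 = 2.3; Standard 325/125 = 2.6.
- Pooled mean = (1 − s) × Adapted mean + s × Standard mean, where s is the Standard share of the group.

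| Standard share of (c) | Standard share of (b) | Mean (c) | Mean (b) | Ratio |
|---|---|---|---|---|
| 50% | 50% | 77.5 | 197.5 | 2.5 |
| 75% | 25% | 0.25×30 + 0.75×125 = 101.25 | 0.75×70 + 0.25×325 = 133.75 | 1.3 |
| 25% | 75% | 0.75×30 + 0.25×125 = 53.75 | 0.25×70 + 0.75×325 = 261.25 | 4.9 |

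The within-version ratios are the same in every row. Only the mix moves the pooled ratio.

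**When would the group means reverse?** For (c) to exceed (a) under even spread, 30 + 95·s(c) must exceed 80 + 320·s(a).

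- With no Standard completers, s(c) must exceed 50/95 = 53%.
- With (c) entirely Standard, s(a) must be below 45/320 = 14%.
- If every patient in (c) is at the maximum for that group, the condition is 40 + 160·s(c) > 80 + 320·s(a), and s(a) must be below 120/320 = 37.5% even when (c) is entirely Standard.

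With an equal mix the means are 77.5 (c), 197.5 (b) and (80 + 400)/2 = 240 (a), in the expected order.

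**The case against.** The strongest reply is that the groups do what they literally say. They are defined by share of suggested sessions, with both cuts printed, and on that scale the order is correct. Share of course is a defensible scale: section 3.4.2 presents Adapted as a repackaging of the same cross-cutting and core content, so an Adapted completer has reached the end of a planned course and a Standard patient with two of eight sessions has not. More clock time does not prove more treatment. This stands as a defence of the cut. It does not defend calling the pooled comparison a test of varying doses, given how section 1 uses the word and given that section 4.6 defines no unit.

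A reader might infer that the groups reverse the dose order. The documents do not support that. Order holds within each version and by share of course, and group means reverse only under the strong imbalance shown above. Section 4.6 also plans no trend test across the groups and does not label them low or high dose; any gradient would be drawn by a reader who sets the reruns side by side.

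A reader might also infer that the Aim 3 reruns are distorted because each group compares unequal minutes. That does not follow. Unequal planned length is part of the randomised Adapted–Standard contrast, and the full analysis carries the same five-fold difference.

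Two further limits stand. Minutes are planned, not recorded: section 3.5.1.3 lists only a count of sessions. And groups formed by attendance after randomisation are selected groups on any scale, so reporting by version makes the description clearer but does not make a dose effect causal.

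**Conclusion.** The point holds as one of labelling and reporting in a sensitivity analysis. The pooled Aim 1 attendance groups measure the proportion of the intended course attended. In planned minutes they overlap across versions (Standard at or below half, up to 200; full Adapted course, 80), and differences between pooled groups depend on version mix, with an illustrative high-to-low ratio of mean minutes from about 1.3 to 4.9 against 2.3 and 2.6 within versions.

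This rests on sessions running at planned length, completers meaning a full course, an even spread of sessions within groups, and the mixes chosen. The overlap needs only the first two. Uneven mix is plausible, since Adapted was built to lower a burden that staff had named and section 5 reports substantial turnover, but the documents do not show its direction or size. The primary analysis, the error rate and the sample size are untouched. The change is a worthwhile low-cost improvement rather than a necessary correction.

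**What to change.** In section 4.6:

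- Report the Aim 1 attendance groups separately for Adapted and Standard counties, each against UC-DT in the same counties, alongside any pooled result.
- Label the groups as proportion of intended course attended.
- Replace the sentence on varying doses with one that limits any statement about dose to comparisons within a version.

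In section 4.2, tabulate the dropout stages by version, so that the mix behind any pooled group is visible.

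A pooled scale of planned minutes is not a good substitute: every value above 80 comes from Standard, and version is assigned by county, so such a scale would largely restate version and county.

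The cost is wording and extra tables. Section 3.11 says that session counts per patient were already being logged, so no new data are needed. The real downside is smaller groups, and so less precise estimates, within each version.

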### 3.4.3 UC-DT

In UC-DT, patients begin with usual care for four weeks if their CMHC is randomized to Adapted TranS-C and eight weeks of usual care if their CMHC has been randomized to Standard TranS-C. After the delay, they receive Adapted or Standard TranS-C, also based on the condition to which their CMHC has been randomized (see Figure 2). The decision to compare TranS-C to UC-DT was made in close collaboration with the early CMHC partners. This design aims to strike a balance between (a) including a comparison group to demonstrate the effectiveness of TranS-C in community settings; (b) ensuring that *all* participants receive what we hypothesize to be an active treatment (TranS-C); and (c) maximizing efficiency in terms of study duration, budget, and participants' time investment. Notably, usual care has been the comparison group in several influential studies [72-74].

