#### 3.6.2 Patients

Patient assessments in the immediate TranS-C treatment conditions are completed at pre-treatment, mid-treatment, post-treatment, and six months after treatment (6FU). Patient assessments in the UC-DT

condition are completed at pre-treatment and four or eight weeks after pre-treatment (i.e., post UC-DT), depending on whether their county has been randomized to Adapted or Standard TranS-C, respectively. After the post UC-DT assessment, patients start delayed treatment with TranS-C. They subsequently complete assessments at mid-treatment, post-treatment, and 6FU. Note that patients do not complete a 6FU assessment after the delayed portion of UC-DT. This was a compromise made with CMCH partners, so that patients would not need to wait 7-8 months to receive treatment. See Figure 2 for patient timeline.

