### 3.7 Allocation

CMHCs and patients are randomized through a computerized randomization sequence. We do not stratify during randomizing at the county level. When randomizing patients, we stratify for presence of psychosis or not (current), presence of substance use or not (current) and age ( $\geq 50$  or not), as there is evidence these variables can impact sleep or treatment outcome [50, 83, 84]. Only the facilitators, assessors, and research team (i.e., not CMHCs, providers, or patients) are privy to which CMHCs and patients are allocated to which TranS-C treatment condition (Adapted versus Standard TranS-C). CMHC providers and patients know whether their patients have been randomized to receive the immediate or delayed treatment. The facilitator informs each provider when they can start having sessions. In the immediate condition, the provider is asked to begin sessions as soon as possible. In the delayed condition, the provider is asked to wait until after the patient has completed the post-delay assessment (i.e., approximately four weeks in the Adapted condition or eight weeks in the Standard condition).

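### For Aim 1, the session-count subsets cannot test TranS-C at different doses: they select on attendance after randomization, and the plan does not say which UC-DT patients enter them

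*Combined protocol and SAP*

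**What the plan says.** Section 4.6 (Sensitivity Analyses) states, for its first set, that "the analyses for Aims 1-3 will be conducted with (a) treatment completers", then with (b) "patients who completed more than half the number of the suggested sessions" (more than 2 for Adapted, more than 4 for Standard) and (c) "patients who completed half or fewer of suggested sessions". It gives the purpose directly: "these analyses will test the effectiveness of TranS-C at varying doses". It offers no method for handling selection on attendance and no caution about it. None appears elsewhere in Section 4.

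The Aim 1 contrast in Section 4.3 is coded "0 = UC-DT, 1 = Adapted or Standard TranS-C" and concerns change from pre- to post-treatment. Under Section 3.4.3, "patients begin with usual care for four weeks if their CMHC is randomized to Adapted TranS-C", and for eight weeks if it is randomized to Standard. Section 3.7 says that in the delayed condition "the provider is asked to wait until after the patient has completed the post-delay assessment". Section 3.6.2 adds: "After the post UC-DT assessment, patients start delayed treatment with TranS-C". Section 3.5.1.3 provides for counting the sessions given to every enrolled patient. UC-DT patients will therefore have session counts, but only after their Aim 1 outcome has been measured.

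Section 4.6 does not say whether UC-DT patients are kept whole in each Aim 1 subset or are filtered, nor on what they would be filtered.

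**The concern.** How many sessions a patient attends is decided after randomization and may go with prognosis, motivation, stability of circumstances or early response. Restricting the TranS-C arm to high or low attenders gives a group that randomization no longer balances against UC-DT. During the period that determines the Aim 1 outcome, UC-DT has no corresponding behavior to match on.

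A difference between the high- and low-attendance results then mixes any effect of dose with differences between the kinds of patient who attend. The plan would report that mixture as effectiveness by dose. This matters here because the trial studies a shorter version of the treatment, so readers will look for evidence on how much treatment is enough.

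**Working it through.** **Figures in the plan.** The plan gives no figure for these subsets: no expected attendance and no correlation of attendance with outcome. Section 3.8 supplies arm sizes of 240 immediate TranS-C and 240 UC-DT; (240 + 240) × 1.20 = 576 reproduces its total target. The 240 per arm and the two-sided alpha of 0.05 are used below.

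**Step 1. How could UC-DT enter the Aim 1 subsets?** Three readings are open.

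1. *UC-DT kept whole.* An attendance-selected TranS-C group is compared with an unselected control.
2. *UC-DT filtered on sessions received by the Aim 1 outcome.* The planned count is zero, so no UC-DT patient qualifies for subsets (a) or (b) and no contrast exists there.
3. *UC-DT filtered on later sessions, in delayed treatment.* The control is selected on something that happens after its outcome and may depend on it.

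None of these is a randomized comparison of doses.

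**Step 2. Possible size under reading 1.** Assumptions, none of them in the documents: no true effect of sessions; improvement has SD 1; a normal attendance propensity correlates r with improvement; a share p attends more than half. With c = z(p) and normal density φ:

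- bias in the high subset = r × φ(c) / p
- bias in the low subset = -r × φ(c) / (1 - p)
- standard error = √(1/n_subset + 1/240), taking the SD as 1 within subsets

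At p = 0.6, c = 0.253 and φ(c) = 0.386. The multipliers are 0.386/0.6 = 0.644 and 0.386/0.4 = 0.966. Subset sizes are 144 and 96, giving standard errors of 0.105 and 0.121.

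| r | high subset, bias (SD) | low subset, bias (SD) | false gap (SD) | rejection at 5%, high / low |
|---|---|---|---|---|
| 0 | 0 | 0 | 0 | 5% / 5% |
| 0.1 | +0.06 | -0.10 | 0.16 | 9% / 13% |
| 0.2 | +0.13 | -0.19 | 0.32 | 23% / 36% |
| 0.3 | +0.19 | -0.29 | 0.48 | 45% / 67% |
| 0.4 | +0.26 | -0.39 | 0.64 | 69% / 89% |

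Over p = 0.5 to 0.8 and r = 0.1 to 0.4, the false gap runs from 0.16 to 0.70 SD. A negative r gives the same sizes with opposite signs. The rejection rates apply only when the true effect is zero; the biases and gap are unchanged by adding any constant treatment effect.

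**Step 3. Reading 3.** By simulation at r = 0.3 and p = 0.6, UC-DT was split on later attendance correlated ρ with the same propensity. The biases (high / low) were about 0 / 0 at ρ = 1, +0.10 / -0.15 SD at ρ = 0.5, and +0.19 / -0.29 SD at ρ = 0. Splitting UC-DT removes the bias only if later attendance fully reflects the same propensity.

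**Step 4. What the cut-offs measure.** Aim 1 pools both versions. Four Standard sessions (4 × 50 = 200 minutes, Section 3.4.1) count as half or fewer, while the full Adapted course is 4 × 20 = 80 minutes (Section 3.4.2). The cut-offs are consistent as shares of each intended course, but they do not order patients by contact time.

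**The case against.** **The strongest defense.** These are labelled sensitivity analyses. The main analysis is intent-to-treat (Section 4.1), and the multiplicity-controlled confirmatory tests do not depend on the subsets. Section 4.1 also adds predictors of dropout to the models, which might absorb some selection. Session counts will exist for UC-DT patients, and if the team splits them on a comparable propensity the bias could be small.

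Most of this stands as a limit on the damage. It does not rescue the dose interpretation. Section 4.6 does not state a UC-DT split. Covariates for dropout are not a method for attendance-defined subsets. The sensitivity label does not alter what the plan says the results will mean.

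**Stronger readings that the documents do not support.** A reader might infer that UC-DT patients have no sessions to select on at all, so that only the TranS-C arm can be filtered. Sections 3.5.1.3 and 3.6.2 show otherwise: the absence holds only up to the Aim 1 outcome.

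A reader might also infer that the subsets will certainly show false dose effects, with benefit overstated in completers and understated in low attenders. That requires attendance to be related to improvement in that direction. Section 4.6 itself mentions early responders; if such patients stop because they are better, the sign could reverse.

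Nor should the zero-effect rejection rates be read as a forecast of apparent harm. Section 3.8 plans on an average d of 0.89. Even with the -0.39 SD shift, a constant effect of that size would leave 0.89 - 0.39 = 0.50 SD in the low subset.

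Finally, the UC-DT argument covers Aim 1 only. Aims 2 and 3 compare Adapted with Standard, where patients on both sides have sessions. The concern there is differential selection between a four-session and an eight-session course.

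**Conclusion.** The stated interpretation is wrong for Aim 1. The subsets are formed on post-randomization attendance, the control arm has no planned sessions before its outcome, its handling is unstated, and no available reading yields a randomized comparison of doses. The subsets can therefore show a spurious dose pattern.

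The size cannot be derived from the documents. The +0.06 to +0.26 SD (high) and -0.10 to -0.39 SD (low) are illustrations that rest on no true dose effect, UC-DT kept whole, 60% attending more than half, and r between 0.1 and 0.4. Intent-to-treat conclusions do not change. The correction is worth making because the sentence invites a causal reading on dose and costs almost nothing to remove.

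**What to change.** In Section 4.6:

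- Delete the sentence claiming a test of effectiveness by dose.
- Label the three subsets descriptive and not causal, for Aims 2-3 as well as Aim 1.
- State which UC-DT patients enter each Aim 1 subset. Also define treatment completers, and say whether patients with no sessions belong in subset (c).

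If an attendance-adjusted Aim 1 estimate is wanted, use a complier-average effect of receiving any TranS-C session (at least one), with randomized assignment as the instrument. Sections 3.6.2 and 3.7 make non-compliance one-sided by design.

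A threshold of more than half the sessions would not serve, because it assumes zero effect in everyone below it. If every patient gained 0.5 SD whatever their attendance, that estimator would return 0.5 / 0.75 = 0.67 SD with 75% above the threshold, or 0.5 / 0.60 = 0.83 SD with 60%. Even with any session as the threshold, the exclusion restriction has to be stated and argued: patients know whether they are immediate or delayed (Section 3.7), and workbooks go to participating patients (Section 3.1).

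The cost is a wording change and, optionally, one extra model with wider intervals. Session counts are already planned. The trade-off is that no dose-response claim can be made.

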**Table 1. SPIRIT Depiction of Timing and Measures Collected for Implementation Phase**

[figure not shown]
	Screening	Post-Training	Pre-Treatment	Mid-Treatment	Post-Treatment	6-Months Post-Treatment
Patient						
Sociodemographics			X		X	X
Eligibility Items	X					
PROMIS-SD P	X		X	X	X	X
PROMIS-SRI			X	X	X	X
DSM-5 Cross-Cutting			X		X	X
SDS			X		X	X
Sleep Health Composite			X	X	X	X
PHENX Toolkit			X		X	X
CEQ					X	
Provider						
Sociodemographics		X				
Occupation		X				
Acceptability P		X		X	X	
Appropriateness		X		X	X	
Feasibility		X		X	X	
Number of Sessions					X	

*Note.* Allocation to Adapted or Standard TranS-C occurs at the county level and prior to enrollment of any participants in that county (i.e., patients or providers). Enrollment of patients and allocation to immediate TranS-C or delayed TranS-C (UC-DT) occur after the screening and before the pre-treatment assessment. Enrollment of providers after the training. P = Primary Outcome. PROMIS-SD = PROMIS-Sleep Disturbance; note: PROMIS-SD is only assessed during the pre-treatment assessment if done more than one month after the screening to minimize burden for patients. PROMIS-SRI = PROMIS-Sleep Related Impairment. SDS = Sheehan Disability Scale. CEQ = Credibility/Expectancy Questionnaire

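### In Aim 1, sensitivity set 2 fills missing endpoints only for improved immediate-TranS-C dropouts, so its agreement with a positive primary result is weak evidence of robustness

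*Combined protocol and SAP*

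**What the plan says.** Section 4.6, second set, first asks "whether any patients who did not complete post-treatment or 6FU had achieved meaningful clinical improvement by mid-treatment", judged by a reliable change index on PROMIS-SD. For those patients, "we will define these patients as completers, and we will use their mid-treatment assessment in place of a post-treatment assessment". The scope is broad: "Then, all pre- to post-treatment analyses for Aims 1-3 will be rerun". There is no matching rule for dropouts who had not improved.

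Aim 1 (section 4.3) compares immediate TranS-C, Adapted and Standard combined, with UC-DT from pre- to post-treatment. Section 3.6.2 gives the immediate arm a mid-treatment visit inside that window. Assessments in the UC-DT "condition are completed at pre-treatment and four or eight weeks after pre-treatment (i.e., post UC-DT"). Only after delayed treatment starts does it say of these patients: "They subsequently complete assessments at mid-treatment, post-treatment, and 6FU". Section 3.7 fixes the order: "In the delayed condition, the provider is asked to wait until after the patient has completed the post-delay assessment".

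Table 1 marks PROMIS-SD and PROMIS-SRI at mid-treatment. The SDS row and the "DSM-5 Cross-Cutting" row have no mid-treatment mark, although both are Aim 1 secondary outcomes.

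**The concern.** The rule chooses whom to fill by looking at the outcome, and in Aim 1 it works in one arm. An immediate-arm dropout who looks better at mid-treatment enters the endpoint comparison; one who looks the same or worse does not. No UC-DT dropout can enter, because no usual-care score exists between baseline and endpoint. Even with no treatment effect, some patients cross a reliable-change threshold by chance, and adding only those pulls the TranS-C mean down (lower is better).

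At stake is how the rerun will be read. If the primary result favours TranS-C and set 2 agrees, a reader will take that as support, although the check leans the same way when there is no effect. Section 5 reports substantial turnover of patients and providers, so missing endpoints are a practical matter here.

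Two defects of specification need no calculation. The rerun is to cover all pre-to-post analyses, yet two outcomes have no mid-treatment score to substitute. And a patient with an observed post-treatment score who missed only the six-month visit falls within the literal wording of the rule.

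**Working it through.** **1. The plan's own figures.** The plan gives no number for set 2. Section 3.8 supplies the sample size: 480 × 1.20 = 576 patients, so 576/2 = 288 per arm. I use 20% missing as the protocol's allowance. (As a share of those enrolled, the allowance is 96/576 = 16.7%, which makes the shifts slightly smaller.) The 40% case is an assumption.

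**2. Assumed inputs, not in the documents.** PROMIS-SD reliability 0.90; equal correlation ρ of 0.5 to 0.7 between visits; equal random dropout q in both arms; share h of dropouts with a mid score of 1, 1/2 or 1/4. Scores are in SD units. Reliable-change threshold: c = 1.96 × √(2 × (1 − 0.90)) = 0.877 SD.

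**3. Shift with no true effect.** Pre-to-mid improvement has SD s = √(2(1 − ρ)).
- Share of dropouts crossing the threshold: P = 1 − Φ(c/s).
- Their mean improvement: g = s·φ(c/s)/P, so their pre mean is +g/2 and their mid mean is −g/2.
- A model that keeps all pre scores expects a post score of ρg/2, so each filled score is too low by (1 + ρ)g/2.
- Filled patients' weight in the arm: w = qhP/(1 − q + qhP). The shift is w(1 + ρ)g/2.

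For ρ = 0.6, all dropouts with mid scores: s = 0.894, P = 0.1635, g = 1.350, excess = 1.6 × 0.675 = 1.080. At 20%, w = 0.0327/0.8327 = 0.0393 and the shift is 0.042 SD, from 288 × 0.0327 ≈ 9 filled patients. At 40%, w = 0.0654/0.6654 = 0.0983 and the shift is 0.106 SD.

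| ρ | P | excess | 20% missing: all / half / quarter with mid scores | 40% missing: all / half / quarter |
|---|---|---|---|---|
| 0.5 | 0.190 | 1.070 | 0.049 / 0.025 / 0.013 | 0.120 / 0.064 / 0.033 |
| 0.6 | 0.164 | 1.080 | 0.042 / 0.022 / 0.011 | 0.106 / 0.056 / 0.029 |
| 0.7 | 0.129 | 1.074 | 0.034 / 0.017 / 0.009 | 0.085 / 0.044 / 0.023 |

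Simulation of the planned two-occasion random-intercept model agrees: 0.03–0.05 / 0.02–0.03 / 0.01 and 0.08–0.12 / 0.04–0.06 / 0.02–0.03. Reliability of 0.85 to 0.95 widens the all-with-mid-scores figures to 0.025–0.06 and 0.06–0.14.

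**4. False-positive rate (ρ = 0.6, 288 per arm).** The variance per arm is (1 − ρ²)/n_obs + (1 − ρ)²/288. At 20% missing with all mid scores: TranS-C 0.64/239.8 + 0.16/288 = 0.00322; UC-DT 0.64/230.4 + 0.16/288 = 0.00333; SE = √0.00656 = 0.081. The shift is 0.042/0.081 = 0.52 SE, which gives a two-sided rate of about 8.2%. Simulation of 20,000 trials gives 8.0% / 5.6% / 5.3% (all / half / quarter) at 20% and 20.9% / 9.1% / 6.4% at 40%, against 5.0–5.3% without substitution.

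**5. Shift with a true 0.89 SD effect** (the section 3.8 value; ρ = 0.6, all with mid scores). Let T be the total TranS-C-arm improvement and m the part reached by mid-treatment, here T/2. Now P = 1 − Φ((c − m)/s), g = s·φ((c − m)/s)/P, and the shift is w[(1 + ρ)g/2 − (T − m)].

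| Background improvement, both arms | T | P | bracket | shift at 20% | shift at 40% |
|---|---|---|---|---|---|
| 0 | 0.89 | 0.315 | 0.807 − 0.445 = +0.362 | +0.03 | +0.06 |
| 0.5 SD | 1.39 | 0.420 | 0.666 − 0.695 = −0.029 | about 0 | −0.01 |
| 0.75 SD | 1.64 | 0.475 | 0.600 − 0.820 = −0.220 | −0.02 | −0.05 |

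Some background improvement is plausible. Section 3.2 requires a high answer on at least one PROMIS-SD item, and Table 1 notes that "PROMIS-SD is only assessed during the pre-treatment assessment if done more than one month after the screening to minimize burden for patients", so regression toward the mean may fall inside the comparison window.

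**6. Early responders leaving** (simulated; truth 0.89, 20% missing, 40% of improvers dropping out, 13 settings). Primary model 0.82–0.88; set 2 0.82–0.92; three-occasion model with unstructured covariance 0.89–0.90 in the 10 settings where the improvement driving dropout was recorded, and 0.86–0.87 in the 3 where it was only partly recorded.

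**The case against.** The strongest reply has four parts.

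*The effect is small.* At the only attrition figure in the documents the null shift is at most about 0.05 SD under the main assumptions, and 8% false positives requires every dropout to have a mid score. Section 4.2 lists dropout before the first session, so that is an upper bound. This stands, and it is why the point is not a critical one.

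*The direction is not fixed.* A reader might infer that set 2 always flatters TranS-C, or that its agreement with the primary result never means anything. The documents do not support either reading. With a real effect and background improvement the shift vanishes or reverses (step 5). If both analyses are null, the agreement is somewhat informative, because the null shift runs toward TranS-C.

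*The sets serve another purpose.* Section 4.6 offers them to account for the pandemic and the clinic context, and mentions early responders, though under the first set. If early responders leave, the primary model undershoots and set 2 can correct it. It can also overshoot or remain short, so it is not a dependable correction.

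*The alternative also assumes data missing at random.* True. Where improvement before dropout was only partly recorded, set 2 was closer to the truth in two of three settings. The alternative is better where the mid score carries the information; it is not a stress test.

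One could also propose using UC-DT patients' later mid-treatment scores. Those follow the post-delay endpoint and are taken under TranS-C, so they are not usual-care values.

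**Conclusion.** The point holds for Aim 1 and should be acted on. That the fill is one-armed and selected on improvement follows from sections 3.6.2, 3.7 and 4.6 alone, and in every no-effect setting examined the shift was toward TranS-C. The sizes rest on assumed reliability, correlations, dropout pattern and availability of mid scores, so confidence in them is moderate. The practical conclusion is limited: set 2 should not be reported as robustness support for a positive primary result.

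It would be wrong to infer that the primary Aim 1 analysis is biased by this rule; it does not use the substitution. It would also be wrong to extend the point to the Aim 2 provider ratings or to the mediation models as a bias, since none has been shown there. In Adapted versus Standard patient comparisons both arms have mid scores, so only the selection on improvement remains. The gap for SDS and DSM-5 Cross-Cutting and the ambiguity about observed post-treatment scores are plain matters of wording and hold regardless of any assumption.

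**What to change.** For Aim 1, replace the substitution in section 4.6 with text to this effect:

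- The PROMIS-SD and PROMIS-SRI models are refitted with time in three categories (pre, mid, post) and an unstructured covariance across visits. Every available mid-treatment score is entered regardless of improvement. UC-DT contributes pre-treatment and post-delay scores only. The treatment contrast is taken at post-treatment.
- SDS and DSM-5 Cross-Cutting are excluded from set 2 because they are not measured at mid-treatment.
- An observed post-treatment score is never replaced.
- Reliable change on PROMIS-SD among dropouts is descriptive only, which fits the reporting of improvement among dropouts already planned in section 4.2.
- In Adapted versus Standard patient comparisons, any use of mid scores is not conditional on improvement.

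No change to the Aim 2 provider models is needed on this ground. The unstructured covariance matters: under unequal correlations between visits, a random-intercept version gave 0.86 where the unstructured one gave 0.89, the true value. Simply treating every mid score as a post score is not a substitute. It biased the comparison against TranS-C by 0.03 to 0.05 SD at 20% missing when both arms improved by 0.5 SD.

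The cost is SAP wording and modest modelling with data already collected. The downsides are a possibly less favourable sensitivity result and continued reliance on data missing at random, so the refit does not test unrecorded reasons for dropout.
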